Time 1 (T1) Mediator assessments taken weekly during the 10-week intervention, but will only be analyzed for weeks 1, midpoint, and 10. Physiological data (HR, HRV, and EDA) measurements will be taken continuously during the entire intervention lessons. Sections of analysis will be segmented from: (a) Three to five-minute seated art activity baseline before either intervention; (b) 45-minute THR riding or BA activity; (c) 15-minute THR grooming and tacking or BA scrapbook activity; and (d) 5-minutes post intervention that includes a seated art activity. RAs will annotate time and relevant activity levels for each period to correspond to device timestamps. Salivary cortisol samples will be taken during the five-minute seated baseline before THR or BA intervention and again 5 minutes post intervention. Caregivers will complete the Physiological Sample Collection Log each week of the 10-week intervention.

Time 2 (T2) Post- intervention assessments (Visit XIV): On the last day of the 10-week intervention (THR, BA, Hybrid) or waitlist period, caregivers will complete the ABC-C,⁹⁸ SRS™-2,¹²⁶ EDI,¹²⁸ , the WHOQOL-BREF⁹⁵ , and the Crisis Mental Health Care Usage Survey. Within one month of the conclusion of week 10 of the intervention phase, all participants (THR, BA, waitlist, and Hybrid) will be individually scheduled to complete the SALT¹²⁷ with the same speech therapist they saw for the Pre-intervention SALT at the Colorado or Maine hospital site. If there is a speech therapist personnel change from a participant's pre- to post- intervention SALT assessment visit, this change will be noted in the REDCap database to control for personal novelty bias in the analysis.

Time 3 (T3) Six-month post-intervention assessment (Visit XV): Only THR and BA participants will be individually scheduled to complete SALT¹²⁷ with the speech therapist at their study site (Colorado or Maine). During this visit, caregivers will complete the ABC-C,⁹⁸ SRS™-2,¹²⁶ EDI,¹²⁸ , the WHOQOL-BREF⁹⁵ , and the Crisis Mental Health Care Usage Survey. If there is a speech therapist personnel change from a participant's post- to 6-month post- intervention SALT assessment visit, this change will be noted in the REDCap database to control for personnel novelty bias in the analysis.

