Therapeutic Horseback Riding at both study sites (CO and ME): Participants will be required to have a medical clearance form completed and signed by their primary care physician prior to engaging in the THR, BA, or Hybrid activities at the riding center. Horseback riding has inherent risks and this study involves weekly horseback riding lessons. Risks from horseback riding could include fall, loss of consciousness, bodily injury, dismemberment or death. These risks are mitigated by this study's use of a PATH International Premiere Accredited Center. This means that they adhere to national standards to ensure safe and effective operations throughout all areas of programming. More information about these center accreditation standards can be accessed by visiting the PATH International website at www.pathintl.org. In addition, PATH international certified instructors will be conducting the therapy. These instructors have demonstrated PATH competency in the areas of equine management, horsemanship, riding instruction, teaching methodology and knowledge of disabilities. These instructors also have Cardiopulmonary resuscitation (CPR) and First Aid certifications. **(See riding centers' participant rider safety standards and procedures in the Appendix documents.)**

Assessments: This study also involves caregivers completing questionnaires and participants being assessed with diagnostic and cognitive measures. Any results from these assessments of the child, conducted as part of this study, may be uncomfortable for the caregivers to hear; however, these results will be discussed with caregivers in detail, and a written report of the cognitive assessment results provided upon request of the caregiver. The study assessments take a considerable amount of time; therefore, the NVIQ and ADOS-2 assessments may be divided into sessions on different days in order to reduce fatigue and increase compliance. The PI and other study evaluators have extensive experience in the administration of assessments with the proposed study population.

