Adequacy of Protection Against Risks: The risks to participants regarding THR are mitigated by this study's use of two sites that are PATH Intl.¹⁷ Premiere Accredited Centers. Première accreditation status means they follow rigorous standards and comply with site visits every five years to assess the sites' infrastructure as well as ensure safe and effective operations for horses and humans throughout all areas of programming. *More information about these center accreditation standards can be accessed by visiting the PATH Intl. website at www.pathintl.org.* The standard procedures used by the therapeutic riding centers for this proposal decreases risks to the riders and staff implementing safety policies standard in the field and according to PATH Intl. guidelines. Such safety standards include the following: requiring participants wear protective gear, monitoring the temperament of the horses, training horses to participate in therapeutic horseback riding experience with children who have a variety of disabilities, and instructing participants about safe practices around horses. In addition, PATH Intl. certified instructors will be conducting the therapy. These instructors have demonstrated PATH Intl. competency in the areas of equine management, horsemanship, riding instruction, teaching methodology and knowledge of disabilities. These instructors also have Cardiopulmonary resuscitation (CPR) and First Aid certifications. (See riding centers' participant rider safety standards and procedures information in the Appendix documents.)

Participant Discontinuation Criteria: Participants who miss more than two out of the 10 THR, BA or Hybrid intervention lessons will automatically be dropped from the study. Participants who develop significant allergic reactions to conditions at either of the riding centers (CO or ME) will, at the discretion of the caregiver or the riding center staff, be dropped from the study. There are no protocol-stopping criteria as there are no *a priori* hidden risk concerns from which to build criteria. The participant discontinuation criteria will adequately protect study participants.

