General consideration of statistical analysis: Prior to the start of any formal analyses, data for each variable will be examined to identify unusual values that need to be queried, including outliers, patterns of missing values, and non-Gaussian distributions (i.e., have significant skewness and kurtosis). Baseline demographic and clinical characteristics will be summarized using descriptive statistics and grouped by intervention arms. Between-arm difference in demography and baseline variables will be examined using t-test or chi square test respectively for continuous and categorical variables. Any imbalance that could potentially be a confounding factor for the outcome will be adjusted for in statistical models (see below). The primary efficacy analysis will use the “intent-to-treat (ITT)” principle to test our study hypotheses under practical and realistic conditions where not all participants follow or complete the program. All randomized participants will be analyzed in the ITT analyses. Linear Mixed Effect Model (LMM) will serve as the primary method to handle missing values. Other analyses such as completer analysis and analyses with imputed data will be deemed as sensitivity analysis for efficacy examination. However, for mediation analysis, only participants with both the

mediator (intervening) variable and outcome variables available will be included to explore mechanism of the intervention effect. No interim analysis will be conducted. In all analyses, a $p \leq 0.05$ will be considered significant. SAS and Mplus software will be used for these analyses.

AIM1: Efficacy assessment (for H1a-1c): LMM with unstructured covariance will be used to model baseline and end of treatment (EoT or T_2) primary and secondary outcome measures as well as expanded outcomes where fixed effects include evaluation time (baseline or EoT) and intervention arm indicator (THR/BA), as well as their interaction.

[figure not shown]
Estimate of the interaction will be used to quantify effect size and tested for statistical significance.

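### The attendance rule removes children from the study rather than only from lessons, so the ITT analysis loses the post-baseline outcomes it needs

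*Protocol*

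**What the plan says.** Protocol, Participant Discontinuation Criteria, gives two grounds for removal. The first is attendance: "Participants who miss more than two out of the 10 THR, BA or Hybrid intervention lessons will automatically be dropped from the study". The second is a significant allergic reaction, where the child may, "at the discretion of the caregiver or the riding center staff, be dropped from the study". Both take the child out of the study, not only out of the lessons. No section shown describes outcome assessment after removal.

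Protocol, General consideration of statistical analysis, says that ITT is used to test the hypotheses "under practical and realistic conditions where not all participants follow or complete the program", and that "All randomized participants will be analyzed in the ITT analyses". The mixed model is the primary way of handling missing values. Completer and imputed-data analyses are sensitivity analyses.

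The Aim 1 model contains two time points, baseline and end of treatment (T2). The Aim 2 model adds T3, with MCMC imputation of missing T2 or T3 values as a sensitivity analysis.

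On outcome collection, the T2 section says: "On the last day of the 10-week intervention (THR, BA, Hybrid) or waitlist period, caregivers will complete the ABC-C". Waitlist children attend no lessons during their waiting period.

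**The concern.** ITT is chosen because some children will not finish the program, but the attendance rule stops follow-up of exactly those children. An analysis method cannot recover outcomes that the protocol stops collecting.

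The loss need not be alike in the two arms. BA children have no contact with horses during the 10 weeks, and their free ride comes after the post-intervention SALT. Within the THR/BA comparison, absence after a riding injury in that period can therefore arise only in THR. Conversely, the section on Treatment Randomization and Termination expects that BA children may be frustrated at not interacting with horses, which could cause absence in BA. If absent children would have done differently from those who stayed, and the reasons differ by arm, the estimated difference is biased.

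**Working it through.** **1. The rule.** More than two of 10 missed means removal at three or more, so a retained child has attended at least eight lessons.

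**2. What a removed child contributes.**
- Aim 1 model (baseline, T2): the baseline value only.
- Aim 2 model (baseline, T2, T3): the baseline value only.
- MCMC imputation: T2 and T3 are filled from the pattern among children who remain.
- Completer analysis: nothing.

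Each of these relies on children who stayed, or leaves the removed child out.

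**3. The plan's own power figures (Power analysis).** Inputs are d = 0.62 and 5% two-sided (sidedness assumed). The normal approximation gives 97.6% at the 81 per arm shown in Table 2, 95.9% at 71 and 90.7% at 56. The stated 97% (ITT) and 90% (completers) reproduce within two points. The planned loss is 71 − 56 = 15 per arm. If 5% to 20% per arm have no T2 value, power from 71 per arm falls from 95.9% to between 95.0% and 91.1%. Power is therefore not the main issue.

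**4. How many could be removed.** The protocol gives no rate of missed lessons. Assume independent misses with a fixed probability per lesson:

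| Assumed miss rate per lesson | P(3 or more of 10) | Expected number of 71 |
|---|---|---|
| 5% | 1.2% | 0.8 |
| 10% | 7.0% | 5.0 |
| 15% | 18.0% | 12.8 |
| 20% | 32.2% | 22.9 |

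Ordinary absence alone could account for anything from about one child per arm to more than the planned 15.

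**5. Possible bias.** The planning changes in irritability are −6.9 (THR) and −2.3 (BA), a difference of 4.6. Suppose mT and mB children are removed, who would have changed by xT and xB, and the model in effect gives them the mean of their arm's remaining children. Then:

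overstatement of the THR advantage = (mT/71)(xT + 6.9) − (mB/71)(xB + 2.3)

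Removal in THR only (mB = 0):

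| mT | xT = −2.3 | xT = 0 | Share of 4.6 |
|---|---|---|---|
| 1 | 0.06 | 0.10 | 1.4% to 2.1% |
| 3 | 0.19 | 0.29 | 4.2% to 6.3% |
| 5 | 0.32 | 0.49 | 7.0% to 10.6% |

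Two variants show that the sign is open:
- BA only, mB = 5 and xB = 0: −(5/71)(2.3) = −0.16, so the THR advantage is understated.
- xT = −6.9 and xB = −2.3: the bias is zero.

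The values of m and x are assumptions.

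**6. Whether attendance is needed to measure the outcome.** It is not. Waitlist caregivers complete the same T2 forms without any lessons, and T3 is a clinic visit six months later.

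**The case against.** **Points that stand**
- A removed child is not deleted from the ITT set. The mixed model can include the baseline value, and the plan expects missing outcomes and 20% attrition. A reader might infer that the rule breaks the statement that all randomized participants are analyzed. The documents do not support that; the conflict is with the stated purpose of ITT.
- The absence of T2 and T3 data is the plain reading of removal from the study. No sentence says it outright.
- ABC-C is collected weekly, so some irritability scores before removal would exist, and an imputed-data analysis could use them. The Aim 1 model does not, and the T2 and T3 values would still be missing.
- A caregiver may postpone and restart after at most two lessons, so some early absences need not end in removal. Later ones are not covered.

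**Stronger readings the documents do not support**
- *Injured riders have no protection.* The protocol names the hazard ("Risks from horseback riding could include fall, loss of consciousness, bodily injury, dismemberment or death") and says of its criteria: "The participant discontinuation criteria will adequately protect study participants". The criteria do not mention injury. But the protocol also refers to "participant rider safety standards and procedures information in the Appendix documents", which is not shown and may hold rider-level rules, and it describes medical clearance and accredited centers.
- *An injury would be hidden as non-attendance.* The Data and Safety Monitoring Plan requires reporting of adverse events and names falls from the horse, so the reason could be on record.
- *The bias must favor THR.* Step 5 shows that it could go either way or be nil.
- *A safety-only exception would be enough.* It would leave most removals untouched, and it would keep an injured THR child while dropping a BA child who missed the same lessons through illness.

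**Conclusion.** The point holds for absence of any reason in any arm with lessons. Applying the attendance rule as written discards post-baseline outcomes that the ITT analysis is meant to use, and none of the planned analyses recovers them. The comparison may be biased if reasons for absence, and the outcomes of absent children, differ between THR and BA.

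The size is unknown. With one to five THR children removed and the assumed outcomes above, the shift is 0.06 to 0.49 points on a planned difference of 4.6. The documents give no rate of missed lessons or of injury to say which case is realistic. The conclusion also rests on reading removal from the study as the end of assessment. The change should be made because the conflict is clear and the remedy is cheap, not because a large bias has been shown.

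**What to change.** Amend Participant Discontinuation Criteria as follows:

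- Missing more than two lessons, or stopping because of allergy, injury or another safety reason, ends or limits the lessons only.
- Every randomized THR and BA child is still invited to the planned T2 and T3 assessments, timed from week 10 of the assigned group. Waitlist/Hybrid children are invited to T2.
- The reason for stopping is recorded.
- The rule is the same in all arms.
- The eight-lesson threshold is kept only to define the completer sensitivity analysis.

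This uses visits and forms already planned. With Maine closed since December 31, 2023, it would apply at the Colorado center, and children enrolled before and after the amendment would fall under different retention rules.

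The statistical cost is some dilution, because analysed children will include some with fewer than eight lessons. If 5% to 20% of THR children were followed and had no benefit at all over BA, the effect size would fall from 0.62 to between 0.59 and 0.50. Power at 71 per arm would then be 93.9% to 84.0%. That range is a pessimistic illustration, and the estimate would be closer to the one that the ITT statement describes.

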Electrodermal Activity (EDA): The Shimmer3 EDA has been successfully used in studies worldwide involving youth with ASD similar to our target population, and is the frontline instrument used in the lab of our physiology expert co-investigators. Continuous peripheral physiological arousal will be assessed in all participants using Shimmer3 EDA monitor (also known as skin conductance or galvanic skin response). This is a well-established index of sympathetic nervous system arousal.⁴⁰ The Shimmer3 EDA weighs 28 grams (dimensions 3 x 1 ½ x ½ inches), is made of durable plastic materials that make it water resistant and shock proof, and is regulatory compliant. The Shimmer3 EDA monitor records EDA from the ventral area of the wrist using alternating current imperceptibly applied to the skin through two hypoallergenic, durable, and replaceable Ag electrodes. As dry non-adhesive electrodes tend to move on the skin surface during physical activity and destroy signal quality, disposable adhesive electrodes with an appropriate salinity (e.g., 0.5%; EL507) will be used, as biopotential electrodes with higher salinity overestimate tonic skin conductance. EDA sampling frequency in the Shimmer3 is 4 Hz with a 0.01– 100uS range. Peripheral skin temperature is recorded by the Shimmer3 EDA monitor at 4 Hz in the -40 to 115-Celsius range using optical infrared thermopile. Finally, the Shimmer3 EDA records motion-based activity up to ±8g at 32 Hz using 3-axis accelerometry. EDA recordings from the central wrist are well correlated ($r = .574$) with traditional laboratory-based measurements from the fingers.¹²² Although the Shimmer3 EDA assessments will be taken weekly during the 10-week intervention, these assessment data points will only be analyzed for weeks 1, week 5 or the adjacent week if participant misses session 5, and week 10.

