Data Sharing Plan: Study data will be collected and managed using REDCap electronic data capture tools hosted at the University of Colorado.¹³¹ REDCap (Research Electronic Data Capture) is a secure, web-based application designed to support data capture for research studies, providing: (1) an intuitive interface for validated data entry; (2) audit trails for tracking data manipulation and export procedures; (3) automated export procedures for seamless data downloads to common statistical packages; and (4) procedures for importing data from external sources

Physiological data (HR, HRV, EDA) will be monitored on an ongoing basis for quality control throughout the study by physiological activity assessment experts, both visually and using automated quality control software.¹³² Video recordings of 20% of each 10-week intervention will be shared with the intervention fidelity coordinators to rate intervention fidelity. Colorado's site physiological and fidelity video data will be shared through the CU One Drive and Maine site's physiological and fidelity video data will be shared through OpenText. Fidelity videos may also be shared via flash drive mailed via FedEx.

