Data auditing and cleaning: HRV: Following the authoritative guidelines given in the Task Force,¹³³ data will be band-passed filtered (0.5-45Hz), heartbeats will be detected by automatic multiscale-based peak detection,¹³⁴ and lost data and/or premature atrial/ventricular contractions corrected via cubic spline interpolation. Time-domain indices (HR; SD; root-mean square of successive differences, RMSSD) will be calculated per standard methods. Frequency-domain indices (LF, low-frequency power; HF, high-frequency power) will be calculated via Lomb-Scargle Periodogram, and reported as natural log values. Standard covariates will be applied, and data quality reporting indices will be reported.^{135,136} EDA will be decomposed into tonic and phasic activity using standard methods⁴⁰ and de-noised depending on the accelerometer data – periods of high physical activity will be removed from the analysis period. The mean, SD, and non-specific skin conductance responses (NSSCRs; bursts of activity over 0.2uS) will be extracted per time period. NSSCRs will be reported as depolarizations per minute. Signal quality for both physiological records, which is frequently problematic during ambulatory recording, will be maintained through the combined use of automated tools for quality control,¹³² visual artifact identification, and redaction.¹³⁷

During each 10-week intervention (THR and BA), [name] lab team will meet with study PI, [name] and RAs from Colorado and Maine sites to monitor the Shimmer ECG (HR/HRV) and EDA data collected for quality and for possible equipment failure issues. [name] lab team in collaboration with [name] will then determine which data points collected will be used for analyses, ensuring that each subject has a beginning point (Lesson 1 or alternate lesson 2 or 3), midpoint (Lesson 6 or alternate lesson 7), and endpoint = (Lesson 10 or alternate lesson 9 or 8).

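### The lesson that supplies each HR, HRV and EDA value is chosen after the recordings are inspected, with no substitution criterion and no stated masking, and the permitted lessons contradict the measures section

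*Protocol*

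**What the plan says.** The Data auditing and cleaning section describes meetings during each 10-week round. The laboratory team joins the study PI, together with "RAs from Colorado and Maine sites to monitor the Shimmer ECG (HR/HRV) and EDA data collected for quality and for possible equipment failure issues". The laboratory team, in collaboration with one person whose name is removed, "will then determine which data points collected will be used for analyses, ensuring that each subject has a beginning point". The permitted lessons for the first two points are "beginning point (Lesson 1 or alternate lesson 2 or 3), midpoint (Lesson 6 or alternate lesson 7"). For the last point the default is lesson 10, with 9 and 8 as alternates. No condition for moving to an alternate is given.

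The same section specifies filtering, automatic peak detection, interpolation and accelerometer-based removal of EDA. It keeps signal quality through automated tools together with "visual artifact identification, and redaction". The Data Sharing Plan has the signals monitored "by physiological activity assessment experts, both visually and using automated quality control software". Neither place mentions masking to arm.

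The measure descriptions for EDA and for HR/HRV give another rule for the same signals: analysis of week 1, "week 5 or the adjacent week if participant misses session 5, and week 10".

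Under Time 1 (T1) Mediator assessments, the research assistants annotate time and activity in each period of a session. The Physiological Data Interval Recording Log labels those periods by arm (mounted riding or barn lesson, grooming or scrapbook). The only assessor the protocol describes as masked is the speech therapist, in the SALT description.

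**The concern.** The protocol presents HR, HRV and EDA as objective measures of mechanism. They carry H1c and, with cortisol, H1d. The value analysed for a child depends on which lesson is taken and which stretches of signal are kept. Both decisions follow a look at the recordings, in a process attended by people who see the arm. If substitution or redaction differed by arm, even unintentionally, it could create or hide a THR effect on physiology.

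The mediation plan would carry such an error forward. Mediators are screened on path a, and only those that are significant go on to path b and the indirect effect. Two incompatible lists of admissible lessons widen the room for judgement.

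**Working it through.** **The two rules side by side (HR, HRV, EDA)**

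| Point | EDA and HR/HRV measure descriptions | Data auditing and cleaning |
|---|---|---|
| Start | Week 1, no alternate | Lesson 1, or 2 or 3 |
| Midpoint | Week 5, adjacent week if session 5 is missed | Lesson 6, or 7 |
| End | Week 10, no alternate | Lesson 10, or 9 or 8 |

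The midpoint defaults differ. Only the first rule ties an alternate to an event.

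**Inputs.** Expected data retention is 85% (conclusions of the THR feasibility pilot). The completer or mediation sample is 56 per arm, with a = 0.4 and b = 0.43 (Power analysis). Assumed here: recording losses are independent across lessons, lesson values are normal, and there is no true change. A lesson SD is the within-child SD between lessons.

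**The plan's nearest figure.** The protocol gives no number for lesson selection. The closest is 90% power for the indirect effect with N = 112.
- SE_a = √((1 − 0.4²)/112) = 0.0866.
- SE_b = √((1 − 0.43²)/(112 × (1 − 0.4²))) = 0.0931.
- Sobel z = 0.172/√(0.4² × 0.0931² + 0.43² × 0.0866²) = 3.27, so power = Φ(3.27 − 1.96) ≈ 90%.

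This reproduces the stated figure. The calculation makes no allowance for selection of the mediator values.

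**Lesson sets permitted per child.** 3 × 2 × 3 = 18 in all; 3 × 3 = 9 for start-to-end change; 3 × 2 = 6 for start-to-midpoint change.

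**How often an alternate would be needed**
- Two-point change score: 1 − 0.85² = 28%. The limits are 15% if losses coincide fully and 15% + 15% = 30% if they never coincide.
- All three points: 1 − 0.85³ = 39%.

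The pilot's 15% loss came from equipment, cooperation and noise, recorded with devices other than the Shimmer3 monitors now planned. Missed lessons would come on top.

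**Worst-case bound.** The expected maximum is 3/(2√π) = 0.85 SD for three standard normal values and 1/√π = 0.56 SD for two.
- Start to end, most favourable of three at both ends: 0.85 + 0.85 = 1.7 lesson SDs.
- Start to midpoint, three and two candidates: 0.85 + 0.56 = 1.41 lesson SDs.

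**Limited case.** Suppose alternates are used only when the default is lost (15%), and in one arm only the more favourable of two alternates is taken.
- Start to end: 0.15 × 0.56 × 2 = 0.17 lesson SD. Divided by the SD of change, √2 lesson SDs, this gives a spurious d of about 0.12.
- Start to midpoint: the midpoint has a single alternate, so only the start offers a choice. 0.15 × 0.56 = 0.085 lesson SD, or d of about 0.06.

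A null simulation of start-to-end change (56 per arm, 4,000 replicates, between-lesson correlation 0.5, 0.7 and 0.9) gave d of about 0.12 and rejection rates of 10.7%, 9.0% and 10.2% against a nominal 5%. With free best-of-three selection at both ends in one arm, d was about 1.37 and the null was rejected essentially always. A fixed rule applied without knowledge of arm would keep the nominal 5%.

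**The case against.** The text supports a milder reading on several counts.

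- **Who decides.** The research assistants are named for the quality meetings, not for the selection, which rests with the laboratory team and one collaborator. Whether that collaborator knows the arm cannot be read from the text. That the research assistants see the arm is a fair inference from their duties, but it is not stated. The redaction sentence names no actor, and the Data Sharing Plan points to physiology experts. A reader might infer that unmasked site staff pick lessons and delete signal; the document does not say so.
- **How free the choice is.** Each point has a default, the others are called alternates, and they run outward from the default. The stated purpose is quality and completeness. The natural reading is default first, alternate when it is unusable.
- **Safeguards.** Much of the processing is automated, and data quality indices are to be reported.
- **Where detail belongs.** Numeric thresholds, masking of signal reviewers and a lock before merging often sit in a SAP, which is not shown. Their absence carries little weight by itself.

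All of this narrows the point. What remains is that the protocol itself sets a selection procedure, runs it on inspected recordings during each round, gives no condition for substitution, and contradicts its own rule elsewhere.

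**Conclusion.** The point holds as a weakness in procedure, with bias possible but not shown. It is confined to HR, HRV and EDA under H1c and H1d. Caregiver-rated ABC-C irritability and the cortisol assays do not pass through this selection.

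The discretion would reach about 28% of two-point change scores, assuming 85% retention and independent losses. A between-arm error further requires that selection or redaction differ by arm. If alternates replace only lost defaults, the distortion is modest even when every such choice favours one arm.

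A reader might take the 1.7 lesson-SD figure as the likely error, or conclude that the measures lose their objectivity. Neither follows. The figure assumes the most favourable of three lessons at both ends for every child and falls to 1.41 for start to midpoint. The named defaults and automated processing also limit what judgement can do. The change is worth making because it is cheap and the recordings are already taken weekly.

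**What to change.** 1. Reconcile the Data auditing and cleaning section with the EDA and HR/HRV measure descriptions into one ordered list of lessons per time point.
2. Use the first listed lesson that passes a pre-set automated quality score.
3. Do visual redaction on files with arm and lesson number removed, at least for the seated segments. Motion in the lesson segments may reveal the arm whatever the label.
4. Lock the selected lessons before any outcome is merged.
5. Report substitutions and redactions by arm.
6. Add a sensitivity analysis using default lessons only.

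The cost is some file relabelling, a written rule and less discretion for the laboratory. No new data are needed. The default-only analysis will be smaller: on the figures above it keeps about 0.85² = 72% of two-point change scores.
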